11.4.3. Surgery (\leq 3 months from Baseline Visit)

All procedures are to be performed with either Xenform or native tissue repair, depending on which group the subject has been assigned. Concomitant procedures including posterior repair or sling placement for stress urinary incontinence can occur, per physician discretion. All concomitant procedures will be documented.

- Study procedure
- Cystoscopy, if clinically necessary
- Estimated blood loss [i.e., the total blood loss for the index procedure and concomitant procedure(s) combined]
- Documentation of concomitant procedures
- Document anesthesia type
- Document duration of procedure [i.e., the total duration for the index procedure and concomitant procedure(s) combined]
- Assessment of adverse events (device, procedure, and pelvic floor related)

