Study Design	
Non-randomized, parallel cohort, multi-center study.
 
All procedures will be standardized for uniformity. Physicians will have to document a minimum of 10 procedures with either Xenform or a similar biologic graft or with native tissue repair prior to study participation in order to document competency and experience. Physician training, specialty, and site procedure location (such as private-practice, hospital, academic medical center, etc.) will be recorded.
 
Concomitant procedures including anterior and posterior vaginal wall repair, hysterectomy, and sling placement for stress urinary incontinence may be performed, per physician discretion. Sling placement can include a synthetic material, however a concomitant anterior or posterior repair cannot include a biologic graft or a synthetic implant. An anterior colporrhaphy may be required for cystocele repair, if clinically necessary. All concomitant procedures performed will be recorded.
 
Subjects who undergo a medical intervention (surgical or non-surgical) to treat recurrence, persistence of pelvic organ prolapse or a treatment complication will be followed to 36 months from the initial study procedure.

Planned Number of Subjects	Approximately 454 subjects enrolled (227 subjects per arm). Eligible control subjects meeting the study inclusion/exclusion criteria may be shared from the PFD Registry.

Postmarket Study PS120081: A Prospective, Non-Randomized, Parallel Cohort, Multi-Center Study of Xenform vs. Native Tissue for the Treatment of Women with Anterior/Apical Pelvic Organ Prolapse	
Planned Number of Investigational Sites / Countries	Up to 40 study centers

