The primary endpoint will be assessed once all per protocol subjects have completed the 36 month study visit. All per protocol subjects will be followed to month 36, until study completion, or until discontinuation prior to month 36. All study procedures will be standardized for uniformity. Prior to enrolling a subject, physicians must have completed a minimum of 10 procedures (defined for each arm) in order to document competency and experience. For the native tissue arm, physicians must have completed a minimum of 10 transvaginal anterior-apical prolapse repair procedures that incorporate an apical vault suspension utilizing either a uterosacral ligament suspension or sacrospinous ligament fixation. For the Xenform arm, physicians must have completed a minimum of 10 native

tissue repair procedures (as defined for the native tissue arm) augmented with a biologic graft or Xenform, and the uterosacral and/or sacrospinous ligaments must be accessed via the anterior compartment incision. Physician training, specialty, and site procedure location (such as private-practice, hospital, academic medical center, etc.) will be recorded.

All efforts will be made to ensure all follow-up anatomic measurements (POP-Q) will be assessed by a healthcare provider to reduce surgeon bias on outcomes after the index procedure. In the event the treating surgeon is the only qualified healthcare provider at the site trained in POP-Q assessments, the follow-up anatomic measurements will be performed by the treating surgeon.

All enrolled subjects will have an anterior and/or apical defect. Concomitant procedures to treat a secondary defect can occur (including an anterior repair, posterior repair, hysterectomy, or sling placement for stress urinary incontinence) at the time of prolapse repair for the primary defect, per physician discretion. Sling placement may include a synthetic material yet a concomitant anterior repair or posterior repair cannot include a biologic graft or a synthetic implant. An anterior colporrhaphy may be required, if clinically necessary. All concomitant procedures performed will be recorded.

Subjects who undergo a medical intervention (surgical or non-surgical) to treat recurrence, persistence of POP, or Xenform or suture complication will be followed to month 36 from the initial study procedure.

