12.1.2.3. Statistical Methods

A comparison of data for all subjects will be included per the following statistical analyses to measure for secondary endpoints:

- Rate of adverse device or procedure related events within 6, 12, 18, 24 and 36 months
- Overall rate of adverse device or procedure related events within 6, 12, 18, 24, 36 months
- Comparison of adverse device or procedure related events between treatment groups
- Rate and severity of Xenform exposure and erosion within 6, 12, 18, 24, 36 months
- Assessment of rate of adverse device or procedure related events in subjects with reoperation for failed prolapse repair
- Assessment of rates of/times to reoperation
- Comparison of rate of adverse device or procedure related events in subjects with re-surgery in both treatment groups
- Assessment and comparison between groups of analgesic intake and pain scoring at post-operative 6 weeks, 12, 18, 24, 36 months. Pain score improvement will be analyzed with a paired t-test for each group on all patients and with the propensity score adjusted confidence intervals for the pain score differences between groups. Change in analgesic intake from baseline will be analyzed by McNemar's test for each group on all patients.
- Assessment of severe blood loss during surgical procedure
- Duration of surgery from operative report
- Assessment of re-treatment interventions (i.e. surgery, office-procedure, etc.)
- Assessment of days to discharge and return to normal activity
- Assessment of risk factors, including menopausal status, estrogen use, age smoking, diagnosis of diabetes, body mass index, concomitant procedures, surgeon training and experience

A comparison of data between baseline and 36 months for all subjects will be included per the following statistical analyses to measure for secondary endpoints:

- Quality of Life Assessments (PFIQ, PFDI, PISQ, TOMUS) at 6, 12, 18, 24, 36 months as compared to baseline: paired t-test will be used to compare mean QOL score improvement from baseline to 6, 12, 18, 24 and 36 months for each group.
- Comparison of Quality of Life Assessments improvements between treatment groups
- Assessment of Quality of Life in subjects with re-surgery after re-surgery
- Assessment of subject satisfaction at 6, 12, 18, 24, 36 months (PGI-I for Prolapse)

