12.2.3. Propensity Score Methodology

Analyses comparing the treatment groups will be adjusted for the propensity score. The propensity score is the probability that the subject enrolled in the mesh arm rather than the native tissue (control) arm, given the characteristics of the subject and center. The characteristics identified are as follows: age, race, body mass index, smoking, diabetes, post-menopausal, prior prolapse repair, prior hysterectomy, estrogen use, POP-Q C measurement, POP-Q Ba measurement, POP-Q Bp measurement, concomitant repair for stress urinary incontinence, and surgeon case volume. Logistic regression of both treatment arms (i.e., (transvaginal biologic mesh repair vs. native tissue repair) on these characteristics will be used to estimate the propensity score. The subjects will then be partitioned into five strata corresponding to quintiles of the propensity score. If the balance between treatment arms within the strata is deemed adequate, the treatment difference adjusted for propensity score stratum will be estimated as described in the following.

The propensity adjusted treatment difference will be based on averaging the treatment differences of the propensity score strata. For a binary outcome, the within-stratum treatment difference is $D_j = p_{T_j} - p_{C_j}$, where p_{T_j} and p_{C_j} is the proportion of treatment and control subjects, respectively, in stratum j . The variance of D_j is approximately

$$V_j = \frac{p_{T_j}(1 - p_{T_j})}{n_{T_j}} + \frac{p_{C_j}(1 - p_{C_j})}{n_{C_j}}$$

Denoting the number of subjects in stratum j by $n_j = n_{T_j} + n_{C_j}$, the treatment difference will be estimated by the (weighted) mean of the within-stratum treatment differences

$$D = \sum_j \frac{n_j}{n} D_j$$

where $n = \sum_j n_j$ is the total sample size across all strata and study arms. D is approximately normally distributed with variance

$$V = \sum_j \left(\frac{n_j}{n}\right)^2 V_j$$

from which a confidence interval for the true treatment difference will be constructed. For each continuous outcome, the confidence interval will be constructed similarly, with D and V obtained as above with the treatment difference within each stratum replaced by $D_j = \bar{X}_{T_j} - \bar{X}_{C_j}$, where \bar{X}_{T_j} and \bar{X}_{C_j} , respectively, is the mean of the treatment and control subjects, and

$$V_j = \frac{S_{T_j}^2}{n_{T_j}} + \frac{S_{C_j}^2}{n_{C_j}}$$

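### Arm differences in operating time and blood loss, recorded only as index-plus-concomitant totals, may be confounded by added operations that the propensity model leaves out

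*Combined protocol and SAP*

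**What the plan says.** Section 11.4.3 records operating time as one figure: "Document duration of procedure [i.e., the total duration for the index procedure and concomitant procedure(s) combined". Blood loss is taken the same way: "Estimated blood loss [i.e., the total blood loss for the index procedure and concomitant procedure(s) combined". No index-only time or blood loss is collected. The same section adds "All concomitant procedures will be documented", so the operations each woman had are known.

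The choice of added operations is wide. The synopsis (Study Design) says "Concomitant procedures including anterior and posterior vaginal wall repair, hysterectomy, and sling placement for stress urinary incontinence may be performed, per physician discretion", and Section 8 repeats the list. Section 10.1 assigns each physician to a single arm, even at sites that contribute to both.

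Section 12.1.2.3 opens its list with "A comparison of data for all subjects will be included per the following statistical analyses to measure for secondary endpoints". The entries include "Duration of surgery from operative report" and an assessment of severe blood loss, for which no threshold is given. Neither entry has a test or model. The end of that section sends continuous variables to the propensity-adjusted intervals, and Section 12.2.3 applies the score to analyses comparing the groups. Its covariate list ends with "concomitant repair for stress urinary incontinence, and surgeon case volume". The list also holds prior hysterectomy, prior prolapse repair and POP-Q C, Ba and Bp, but not concomitant hysterectomy, posterior repair or anterior repair. The multivariable models of Section 12.3.10 run within each arm and name other outcomes.

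**The concern.** An added hysterectomy or posterior repair is more than a risk factor for a longer operation: its minutes and its blood are part of the recorded outcome. Treatment is not randomized, and a surgeon's habits about adding procedures stay in that surgeon's arm. If one arm's surgeons add more operations, that arm looks slower and bloodier for reasons unrelated to the graft. If the control surgeons add more, a real cost of placing the graft can be hidden. Because index-only figures are not collected, the separation has to be made in the analysis, and the plan makes it for sling surgery alone.

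The protocol treats the matter as relevant elsewhere. Concomitant procedures are listed as a risk factor in Sections 11.4.2 and 12.1.2.3, Section 19.6 names concomitant hysterectomy in connection with mesh complications, and Section 12.3.5.1 separates women with and without sling surgery when analysing pain. Nothing comparable is planned for duration or blood loss.

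**Working it through.** **Size of the comparison.** The plan gives no sample size, mean or SD for operating time or blood loss. Its effectiveness calculation (Section 12.1.1.2: 70% success in both arms, margin 12%, one-sided 0.05, power 80%) reproduces: (1.645 + 0.842)² × 2 × 0.70 × 0.30 / 0.12² = 180.3, so 181 per arm. With 20% loss, 181 / 0.80 = 226.3, so 227 per arm. Surgery-day outcomes should be available for about all 227.

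**Bias before adjustment.** False difference = (arm difference in the share with the added operation) × (minutes it adds). For example, 10 points × 30 min = 3.0 min; 20 points × 45 min = 9.0 min; 0 points = 0 min.

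**Bias after the planned adjustment.** The quintile estimator of Section 12.2.3 was simulated with 227 per arm, 300 runs per scenario and a true graft effect of zero. Everything else is assumed, because the documents give no values:
- an omitted operation done in about 40% of women, adding 20 or 45 minutes;
- sling in 40%, adding 30 minutes;
- residual SD 30 minutes;
- a score containing sling, one baseline proxy and two noise covariates;
- a proxy correlated 0 or 0.5 with the underlying tendency to have the omitted operation;
- a two-sided 90% interval, borrowed from the primary endpoints, since no level is stated for duration.

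Entries are the mean false difference in minutes, with the share of intervals excluding zero in brackets.

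| Imbalance (points) | Minutes added | Proxy 0 | Proxy 0.5 |
|---|---|---|---|
| 0 | 20 | 0.1 (6%) | 0.0 (7%) |
| 0 | 45 | 0.5 (10%) | 0.5 (6%) |
| 10 | 20 | 2.1 (16%) | 1.4 (13%) |
| 10 | 45 | 4.8 (34%) | 3.6 (26%) |
| 20 | 20 | 3.8 (33%) | 3.2 (23%) |
| 20 | 45 | 9.0 (83%) | 7.1 (61%) |
| 30 | 20 | 6.2 (62%) | 4.6 (38%) |
| 30 | 45 | 13.2 (99%) | 10.6 (94%) |

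The nominal exclusion rate is 10%. At zero imbalance the true bias is zero by construction, so the small values there are simulation error.

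**With the omitted operation included.** Adding it to the score brought the false difference below 0.6 minutes in every scenario, with 3% to 10% of intervals excluding zero. A linear regression on arm, sling and the operation gave at most 0.35 minutes in either direction and 5% to 13% exclusion. The Monte Carlo standard error of a 10% rate over 300 runs is √(0.10 × 0.90 / 300) = 1.7 points.

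**Blood loss.** No calculation is possible. The plan names only severe loss, without a threshold, so the argument there is qualitative.

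**The case against.** The strongest reply is that the plan never sets out a formal between-arm test of operating time. Section 12.1.2.3 says outright that groups are compared for adverse events, pain and quality of life, but duration is a bare entry and blood loss only an assessment. Neither is among the eight secondary endpoints of Section 7.2, and neither has a hypothesis, margin or sample size. This stands in part. The comparison is read from the heading of the list and the general propensity rules, which limits the importance of the point without removing it.

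The existing adjustment also does some of the work. A woman with a prior hysterectomy will generally not need another, and Bp describes the posterior wall. But these are partial proxies: in the 20-point, 45-minute case a proxy correlated 0.5 lowered the bias only from 9.0 to 7.1 minutes. Prior hysterectomy also does not show which women with a uterus had it removed at the index operation.

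Total time can be defended as the cost of each surgical strategy as practised. Section 8.2.2 allows anterior colporrhaphy as part of the control procedure, while Section 8 calls anterior repair concomitant, so the boundary between index and added work may differ by arm. Adjustment also changes the question, because it removes any effect the graft has on the use of added procedures. Both points stand, and they are reasons to report both figures.

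A reader might infer that the planned result shows the mix of operations instead of the graft. The documents do not support that: they show no imbalance, and where one exists the result blends the two. Nor does days to discharge share the measurement problem, since Section 11.4.4 records the date and time of discharge and not a combined total.

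**Conclusion.** The point holds as possible confounding of two supportive outcomes. Following the plan leaves concomitant hysterectomy and posterior and anterior repair outside the adjustment of outcomes to which they contribute directly, and one arm per physician makes an imbalance plausible. Its size is unknown. On the assumed inputs above, the planned analysis would carry roughly 1 to 9 minutes of false difference at an imbalance of 10 to 20 points, and close to none if the mix is similar. It would be wrong to conclude that the comparison is certainly biased or that it can say nothing about the graft; without the mix by arm, a reader cannot tell which case applies. No primary or listed secondary endpoint depends on this, so it is a low-cost improvement and not a threat to the study's conclusions.

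**What to change.** In Section 12.1.2.3:

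1. Tabulate concomitant hysterectomy, posterior repair, anterior repair and sling by arm.
2. Compare duration and severe blood loss (with its threshold stated) by regression on treatment arm, propensity stratum and indicators for concomitant hysterectomy, posterior repair and sling, plus anterior repair where it is not part of the index procedure.
3. Add a comparison among women with no added procedure, if numbers allow.
4. Keep the total-based comparison alongside as the cost of the whole operation, and state that the duration taken from the operative report is the combined total of Section 11.4.3.

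Days to discharge may be given the same adjusted analysis, though it is not a combined-total measure. The cost is SAP wording and a little programming, with no new data. The adjusted figure leaves out any effect of the graft on how often procedures are added, which is why both figures are shown. The restricted comparison may be small; the documents give no frequencies from which to judge.

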11.4.4. Discharge

The subject may be discharged from the hospital and/or treatment facility per standard of care and/or at the Investigator's discretion. Before the subject is discharged, the following assessments must be completed.

- Assessment of infection (wound, vaginal, bladder)

- Assessment of voiding status at discharge (i.e., subject discharged with indwelling catheter or performing self-catheterization to empty bladder or date/time of first void)
- Date and time of discharge
- Assessment of adverse events (device, procedure, or pelvic floor related)

11.4.5. Follow-Up

Subjects will be scheduled for follow-up visits as outlined in Table 11.1-1 (Data Collection Schedule). The follow-up visit schedule begins from the day of the study surgery and includes visit windows (counted in calendar days).

Every effort should be made to do the follow-up visit within the window; however, if this is not possible, the site should attempt to complete the visit as soon as possible but before the next visit window opens. Follow-up visits will be considered missed once the visit window for the next follow-up visit opens. For the Month 36 visit, the visit is not considered missed until the last day of the visit window (i.e., +12 weeks).

Every effort should be made to conduct the follow-up visit at the study site location. However, if the subject cannot physically return to the site for any reason, the follow-up visit may be conducted at the subject's home with their consent and if allowed by local institutional policy and the IRB/EC. If a home visit is not possible, every effort should be made to conduct as much of the visit as possible by phone (i.e., assess adverse events, risk factors, and analgesic intake) and to send the subject questionnaires by mail for completion.

11.4.6. Month 2 Visit (± 4 Weeks)

- Pelvic exam with vaginal length measurement
- Assessment of infection (vaginal, bladder)
- Prolapse grading (POP-Q Scoring)
- Assess pelvic floor symptoms (PFDI-20)
- Assessment of pain (TOMUS pain scale) and analgesic intake
- Assessment of adverse events (device, procedure, and pelvic floor related)
- Assessment of risk factors

11.4.7. Months 6 (± 4 weeks), 12, 18, 24, 36 Visits ($-4/+12$ weeks)

- Pelvic exam with vaginal length measurement
- Assessment of infection (vaginal, bladder)
- Prolapse grading (POP-Q Scoring)
- Assessment of pain (TOMUS pain scale) and analgesic intake
- PFDI-20

- PFIQ-7
- PISQ-12
- PGI-I for Prolapse
- SSQ-8 for surgical satisfaction (Months 6, 12, 24, 36 only)
- EQ-5D for health status (Months 12, 24, 36 only)
- Assessment of adverse events (device, procedure, and pelvic floor related)
- Assessment of risk factors
- Study completion (Month 36 only)

All subjects who have completed the study surgery and discharge will proceed to be followed through the above-outlined study visits to Month 36 where the primary endpoint analysis will be achieved when the last subject completes this visit. All subjects completing the Month 36 visit will be considered to have completed the study.

11.5. *Re-Intervention/Re-Surgery*

It is the intention of this study to demonstrate an improvement in anterior/apical pelvic organ prolapse through clinical effectiveness of transvaginal prolapse repair with Xenform. However, it is recognized that during the course of the study, there is a possibility subjects may require a medical re-intervention for events including but not limited to failed prolapse repair, persistence of prolapse symptoms, or Xenform or procedure-related complication. A re-intervention may include surgical or non-surgical treatments and can occur for a medical complication or for prolapse recurrence. For the purpose of this study surgical interventions shall be classified as “re-surgery” and non-surgical interventions shall be classified as “re-interventions”. Analyses will be performed to compare the rate of office-based interventions and of surgical interventions for medical complications and for prolapse recurrence in both treatment groups.

Non-surgical interventions (re-interventions) are defined as office-based procedures and do not involve an operating room procedure. Examples of non-surgical interventions may include but are not limited to an office visit to trim exposed Xenform or suture in the vagina, a pessary, or physical therapy to treat procedural complications or persistent prolapse symptoms. Data on non-surgical interventions will be captured in the CRFs. Subjects will continue to be followed per the regular study visit schedule.

Surgical interventions (re-surgery) are surgical operations performed to correct recurring prolapse symptoms, a procedural complication, or Xenform-related complication. These surgical events typically may occur on an outpatient basis yet can require admission to a hospital. The decision to perform a re-surgery for failed prolapse repair or persistence of prolapse symptoms will be per physician and subject discretion and all re-surgery data will be captured in the Case Report Forms. All subjects defined as having a prolapse recurrence will be those who have anatomic and symptomatic failure of their prolapse surgery (prolapse beyond the hymen and symptoms of vaginal bulge).

Subjects undergoing a re-surgery will be followed to 36 months post their initial study procedure as indicated in Table 11.1-2. The subject should return to the clinic for the next regular study visit as per her original schedule. If the subject elects to not undergo re-surgery, then the subject will be followed to the Month 36 visit unless the subject chooses to withdraw consent from the study. No subject will be followed for more than 36 months beyond their initial study procedure.

11.6. *Subject Death*

If any serious adverse event results in death (regardless of relatedness to the study device, procedure, or pelvic floor), the event is to be documented in the source documentation, Case Report Form, and reported to the Sponsor within the timeframe noted in Table 21.6-1 (Investigator Reporting Requirements). If an autopsy is conducted, a copy of the final autopsy report should be submitted to the Sponsor or designee. The primary objective of the autopsy is to determine the cause of death, complications and other relevant findings.

12. Statistical Considerations

12.1. *Endpoints*

